## **4.2 Inclusion Criteria**

Subjects must meet all of the following inclusion criteria to be eligible for enrolment into the study:

1. Subject's written informed consent obtained prior to any study-related procedure;
2. Able to understand the study procedures, the risks involved and ability to be trained to use correctly the inhalers and to generate sufficient PIF (at least 40 L/min) using the In-Check device set as per NEXThaler® inhaler resistance and Placebo inhaler;
3. Male subjects aged 30 to 55 years inclusive;
4. Body mass index (BMI) within the range of 18 to 35 kg/m^2 inclusive;
5. Non- or ex-smoker who smoked < 5 pack years (pack-years = the number of cigarette packs (20 cigarettes) or equivalent per day times the number of years) and who stopped smoking > 1 year prior to screening;
6. Good physical and mental status, determined on the basis of the medical history and a general clinical examination, at screening and before treatment;
7. Vital signs at screening within limits defined as: Diastolic Blood Pressure 40-90 mmHg and Systolic Blood Pressure 90-140 mmHg, (three) measures performed in supine position after at least 5 minutes of resting. The average from triplicate measurements must be within the defined range;  
*Note: In case the values are outside the defined ranges, the assessment can be repeated once before treatment.*
8. 12-lead digitised Electrocardiogram (12-lead ECG) in triplicate considered as normal (40 ≤ Heart rate ≤ 110 bpm, 120 ms ≤ PR ≤ 210 ms, QRS ≤ 120 ms, QTcF ≤ 450 ms) at screening visit. The average from triplicate measurements must be within the defined range;  
*Note: In case the values are outside the defined ranges, the assessment can be repeated once before treatment.*
9. Lung function measurements within normal limits at screening: FEV1 >80% predicted and FEV1/FVC > 0.70;  
*Note: In case the values are outside the defined ranges, the assessment can be repeated once before treatment.*
10. Regular bowel movements (averaging one or more bowel movements per day) at screening;
11. Males fulfilling one of the following criteria:
  - a. Males with non-pregnant WOCBP partners: they and/or their partner of childbearing potential must be willing to use a highly effective birth control method in addition to the male condom from the signature of the informed consent and until 90 days after the follow-up visit or

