9.1 Pharmacokinetic Analysis

The concentration ratios of whole blood [^{14}C]-total and [^{14}C]-CHF6001 radioactivity to plasma [^{14}C]-total and [^{14}C]-CHF6001 radioactivity, individual and cumulative mass balance of [^{14}C]-total radioactivity (amount (Ae_u , cumulative Ae_u , Ae_f and cumulative Ae_u) and percentage of dose (fe_u , Fe_u , fe_f and Fe_f) recovered as [^{14}C]-total radioactivity in urine, feces and total excreta) will be calculated by radioanalysis laboratory (██████████).

In addition, metabolites in plasma accounting for $\geq 10\%$ of total radioactivity recovered in this matrix, structural characterization may be performed, where possible. For metabolites in urine and feces (total excreta) accounting for $\geq 10\%$ of total administered radioactivity, structural characterization may be performed, where possible.

If available, fraction of the relevant metabolites in plasma ($\text{Fr}_{\text{plasma}}$), fraction of the relevant metabolites recovered in urine and feces (Fr_{urine} , Fr_{feces} , $\text{Fr}_{\text{urine+feces}}$) will be reported in a separate report together with structural characterization performed by radioanalysis laboratory (██████████).

Urine and Feces [^{14}C]-CHF6001 and [^{14}C]-total radioactivity

Parameter	Units ^a	Definition
Ae_u	mg	amount excreted in urine (expressed in weight) over sampling interval
Cumulative Ae_u	mg	cumulative amount excreted in urine, calculated as the sum of the amount excreted in urine for each collection period
fe_u	%	percent of the dose excreted in urine over a sampling interval
Fe_u	%	cumulative percent of dose excreted in urine, calculated as the sum of the percent of dose excreted in urine for each collection period
Ae_f	mg	amount excreted in the feces over sampling interval
Cumulative Ae_f	mg	cumulative amount excreted in feces, calculated as the sum of the amount excreted in feces for each collection period
fe_f	%	percent of the dose excreted in feces over a sampling interval

Fe _f	%	cumulative percent of dose excreted in feces, calculated as the sum of the percent of dose excreted in feces for each collection period
CL _R	L/h	renal plasma clearance (urine [¹⁴ C]-CHF6001 only)
CL _{R_blood}	L/h	renal blood clearance where CL _{R_blood} = CL _R /R _{b/p} (urine [¹⁴ C]-CHF6001 only)

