E _{h blood}		hepatic extraction calculated from intravenous systemic and renal blood clearance (CL _{blood} = CL/R _{b/p}) and CL _{R_blood} = CL _R /R _{b/p} , respectively and human hepatic blood flow (Q _H ; assumed to be 87 l/h). E _{h blood} = (CL _{blood} - CL _{R_blood})/ Q _H
Cumulative Ae _{u+f}	mg	cumulative amount excreted in urine and feces, calculated as Cumulative Ae _u + Cumulative Ae _f
Fe _{tot}	%	cumulative amount excreted in urine and feces, calculated as Fe _u + Fe _f
Fe _{met}		metabolized fraction calculated as Fe _{met} = [cumulative Ae _{u+f} (¹⁴ C-total) - cumulative Ae _{u+f} (¹⁴ C]-CHF6001)]/ cumulative Ae _{u+f} (¹⁴ C-total)

^a Units are based on concentration units (provided by the bioanalytical lab or preferred units for presentation of PK parameters) and dose units used in the study.

The following PK parameters will be determined by [REDACTED] where possible from the plasma concentrations of CHF6001 following inhaled administration using noncompartmental methods in validated software program Phoenix WinNonlin (Phoenix WNL, Certara, Version 8.1 or higher):

Parameter	Units ^a	Definition
AUC _(0-t) _inh	h*xg/mL	area under the concentration-time curve from 0 to the last quantifiable concentration (t _{last}) ^b
AUC _(0-∞) _inh	h*xg/mL	area under the concentration-time curve extrapolated to infinity ^c
%AUC _{extrap}	%	percentage of AUC due to extrapolation from the last quantifiable concentration to infinity
C _{max_inh}	xg/mL	the value of the maximum observed concentration
t _{max_inh}	h	the time of the maximum observed concentration
t _{last_inh}	h	the time of the last quantifiable concentration
t _{1/2_inh}	h	terminal half-life
F _{inh}		inhaled absolute bioavailability based on AUC _(0-∞)

^a Units are based on concentration units (provided by the bioanalytical lab or preferred units for presentation of PK parameters) and dose units used in the study.

^b Area under the concentration-time curve will be calculated using the linear trapezoidal rule with linear interpolation

^c Based on the last observed quantifiable concentration

The following PK parameters will be determined where possible from the plasma, whole blood, urine and feces [¹⁴C]-CHF6001 concentrations, plasma whole blood, urine and feces [¹⁴C]-total concentrations following intravenous (IV) infusion administration of [¹⁴C]-CHF6001 in each subject using noncompartmental methods in validated software program Phoenix WNL (Certara, Version 8.1 or higher):

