9.4 Calculation of $[^{14}C]$ -CHF6001 and $[^{14}C]$ -total radioactivity Urine Parameters

The amount of the dose administered recovered (Ae_u) in urine as $[^{14}C]$ -CHF6001 for each urine collection interval (t_1-t_2) will be calculated as the product of urine concentration and urine volume. Where only urine sample weight is supplied, a specific gravity of 1 g/mL will be assumed, and it will be considered equivalent to urine volume. A total cumulative $Ae_{u\ 0-x\ h}$ will be calculated by summing across collection intervals over the 0-x h interval, where x = end of the last collection time interval.

The percentage of the dose administered recovered in urine over the time interval t_1 to t_2 ($fe_{u\ t1-t2}$) as $[^{14}C]$ -CHF6001 will be calculated for each urine collection interval as follows:

$$fe_{u\ t1-t2} = (Ae_{u\ t1-t2} / dose_{IV}) \times 100$$

Cumulative fe_u (Fe_u) will be calculated by summing the $fe_{u\ t1-t2}$ values across collection intervals in the same manner as cumulative Ae_u .

Renal plasma clearance (CL_R) will be calculated according to the following formula:

$$CL_R = \text{cumulative } Ae_u / AUC_{(0-\infty)_iv}$$

Alternatively, $AUC_{(0-t)}$ may be used if $AUC_{(0-\infty)}$ cannot be reliably calculated following the formula cumulative $Ae_{(0-t)} / AUC_{(0-t)}$, where 't' is the longest common interval with quantifiable concentrations in plasma and urine.

The fraction of the relevant metabolites recovered in urine calculated as amount recovered (Fr_Urine) will be calculated as follows:

$$Fr_{Urine} = (Ar_u / Dose_{IV}) \times 100$$

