9.5 Calculation of [¹⁴C]-CHF6001 and [¹⁴C]-total radioactivity Feces Parameters

The amount of the dose administered recovered (Aef) in feces as [¹⁴C]-CHF6001 for each faecal collection interval (t_1-t_2) will be calculated as concentration in faecal collected sample and faecal collected sample weight. A total cumulative $Aef_{0-x\ h}$ will be calculated by summing across collection intervals over the 0-x h interval, where x = end of the last collection time interval.

The percentage of the dose administered recovered in feces over the time interval t_1 to t_2 (fe_{f,t_1-t_2}) as [¹⁴C]-CHF6001 will be calculated for each faecal collection interval as follows:

$$fe_{f,t_1-t_2} = (Aef_{t_1-t_2} / Dose_{IV}) \times 100$$

Cumulative fe_f (Fe_f) will be calculated by summing the fe_{f,t_1-t_2} values across collection intervals in the same manner as cumulative Aef.

The fraction of the relevant metabolites recovered in feces calculated as amount recovered (Fr_feces) will be calculated as follows:

$$Fr_{feces} = (Ar_f / Dose_{IV}) \times 100$$

9.6 Criteria for Handling Below the Limit of Quantification or Missing Concentrations for Pharmacokinetic Analysis

Plasma and whole blood concentrations below the limit of quantification will be reported as BLQ in the concentration and parameters tables. All BLQ values will be considered as 0.00 for pharmacokinetic and descriptive statistical analyses.

All concentration data-points with time deviations outside the permitted ranges (see Table in section 7.2.1.1 and 7.2.1.2 of study protocol) will be excluded from the descriptive statistics on plasma, whole blood and urine concentrations, explained by a footnote in the appropriate tables and figures, but kept in PK parameters estimation unless very large deviations not allowing for a proper calculation of PK parameters are found: these cases will be discussed during the Data Review Meeting and decision will be fully documented in the DRR.

General rules to handle missing PK data are detailed below, but a case by case evaluation will be performed during the DRM in order to properly handle every specific situation (e.g., missing values at time points close to expected t_{max}). Decisions will be fully documented in the DRR.

Rules on how to deal with missing values when deriving PK AUC:

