- If intermediate values (not the pre-dose, and not more than 3 consecutive) are missing, they will be considered as missing for the PK analysis and automatically imputed by linear interpolation by Phoenix WNL software.
- If multiple (>1) adjacent values are missing or more than 3 values are missing, then the AUCs will be reported, flagged in the result tables and excluded from the statistical analyses. However, such situations will be discussed case by case at the discretion of the clinical pharmacologist (CP) during the review of the data and fully documented in the DRR.
- If the predose value is missing, then the predose value should be set to “0” for the estimation of the PK parameters. In case of missing predose sample, the Phoenix WNL software will automatically use the value of 0 for the estimation of the PK parameters;
- For an estimation of the urine and stool PK parameters, missing predose value do not affect the final parameter estimates because they are not used in the calculation of A_e .

The following rules apply with special situations defined below:

- If an entire concentration-time profile is BLQ, it will be excluded from PK analysis.
- Where 2 or more consecutive concentrations are BLQ at the end of a profile, the profile will be deemed to have terminated and any further quantifiable concentrations will be set to missing for the calculation of the PK parameters, unless they are considered to be a true characteristic of the profile of the drug.
- If a predose plasma and whole blood concentration is missing, it will be set to 0 by default within Phoenix WNL.

Urine and feces concentrations that are missing or BLQ will be set to zero for the calculation of A_{eu} t_{1-t2} and A_{ef} t_{1-t2} .

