9.8 Presentation of Pharmacokinetic Data

For plasma whole blood and urine concentration data, the following rules will apply:

- Values that are BLQ will be set to 0 for the calculation of summary statistics. In listings BLQ values will be reported as “<LLQ” where LLQ will be replaced with the value for the lower limit of quantification
- Arithmetic mean or median values that are BLQ will be presented as 0.

- If any BLQ results (treated as 0) are in a series of summarized data, geometric mean and CV% of geometric mean will be reported as not calculated (NC).

For PK parameters the following rule will apply:

- Geometric mean and coefficient of variation will not be calculated for t_{last} and t_{max} .

Concentration (mass equivalent in mL or mass in mL)/time curves for plasma total [^{14}C], [^{14}C]-CHF6001 and non-radiolabelled CHF6001 will be presented in linear/linear and log/linear scale. Plots will be presented based on arithmetic means and by subject i.e. all individual plasma concentration/time curves will be presented in one graph.

Arithmetic means (+ SD) showing [^{14}C]-total recovery (Fe_f, Fe_u, Fe_tot in the same graph) and ^{14}C -CHF6001 recovery (Fe_f, Fe_u, Fe_tot in the same graph) over the time will be presented using line charts.

All individual concentration data (mass equivalent per mL or mass per mL) and PK parameters will be listed.

In addition, a listing of the actual sampling times relative to drug inhalation will be provided. Concentrations will be summarized by scheduled sampling time by using n, arithmetic mean, SD, CV, median, minimum and maximum.

For each applicable listing, appropriate flag will be added in case of a concentration reported as ND (i.e., not done) or NS (i.e., no sample) or of value BLQ or for PK parameters not estimated / Not calculated.

10 Safety Analyses

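### SAP 9.6 counts a voided urine or fecal sample with no result as zero drug, and the incomplete recovery total carries no required flag

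*SAP*

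**What the plan says.** SAP 9.6, in its rules for values missing or below quantification, says: "Urine and feces concentrations that are missing or BLQ will be set to zero for the calculation of" interval Ae in urine and feces. It does not separate an interval with no void from one where a void was collected but has no result.

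SAP 9.4 takes urine Ae as concentration times volume, and SAP 9.5 takes fecal Ae from concentration and sample weight. In both, the cumulative amount "will be calculated by summing across collection intervals over the 0-x h interval", with no condition that the intervals be complete. Fe_tot is Fe_u plus Fe_f (SAP 9.1).

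Three provisions soften the rule:
- SAP 9.6 says of missing PK data that "a case by case evaluation will be performed during the DRM in order to properly handle every specific situation", with decisions documented in the data review report.
- SAP 9.8 adds a listing flag "in case of a concentration reported as ND (i.e., not done) or NS (i.e., no sample"), for values below quantification, and for parameters not calculated.
- SAP 7.9.2 requires a footnote when data or subjects are excluded.

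Mean (+ SD) recovery "over the time will be presented using line charts" (SAP 9.8).

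On scope, the sentence in 9.6 names no analyte. The titles of 9.4 and 9.5 name total radioactivity as well as parent drug, and SAP 9.1 lists "plasma whole blood, urine and feces [¹⁴C]-total concentrations following intravenous (IV) infusion administration" among the inputs to the PK analysis. SAP 9.1 also says that the total-14C mass balance "will be calculated by radioanalysis laboratory".

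**The concern.** An empty interval has a true amount of zero. A voided sample without a result has an unknown amount, and setting its concentration to zero gives Ae = 0 whatever volume or weight was recorded. Mass balance and elimination routes are the second study objective, and such a zero can be read as incomplete recovery. Because Ae accumulates, the mean recovery chart stays low from that interval onward.

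Missingness alone does not reveal the problem. Fecal intervals are 24 h, and eligibility asks only for "Regular bowel movements (averaging one or more bowel movements per day) at screening" (Protocol 4.2), so some intervals may properly have no sample. The code NS does not say why there is none.

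The plan is stricter elsewhere. Under SAP 9.6, an AUC with too many missing values is flagged and excluded from the statistics, subject to case-by-case review. A cumulative recovery with a missing interval has no equivalent rule.

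**Working it through.** The documents give no recovery, loss rate or dose share per interval, so there is no planned figure to reproduce. The check is algebraic, with illustrative values.

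**Inputs from the documents.** 8 subjects (SAP 5), with at least 6 evaluable (Protocol 4.4). Nominal IV dose 18.5 µg (Protocol 6.2.2). 13 post-dose urine and 10 post-dose fecal intervals per subject (Protocol 7.2.1.2 and 7.2.1.3).

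**Recovery.** Fe_tot = 100 × (sum of Ae) / Dose_IV. If a voided interval holding m% of the dose is set to zero, the subject's Fe_tot falls by m points (m = 20 is 3.7 µg of 18.5 µg) and the mean of n subjects falls by m/n. If nothing was voided, the error is zero. If the affected subject is otherwise average and the true between-subject SD is s, the observed SD is √(s² + m²/n).

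| m (% of dose) | 1 | 5 | 10 | 20 |
|---|---|---|---|---|
| Subject's Fe_tot if truly 90% | 89 | 85 | 80 | 70 |
| Fall in mean, n = 8 | 0.125 | 0.625 | 1.25 | 2.5 |
| Fall in mean, n = 6 | 0.167 | 0.833 | 1.667 | 3.333 |
| SD, n = 8, s = 3 assumed | 3.02 | 3.48 | 4.64 | 7.68 |
| SD, n = 8, s = 5 assumed | 5.01 | 5.30 | 6.12 | 8.66 |

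**How often.** There are 8 × (13 + 10) = 184 post-dose subject-intervals. If each independently has probability p of a void without a result, the chance of at least one is 1 − (1 − p)^184: 0.168, 0.602 and 0.843 for p = 0.1%, 0.5% and 1%. If 5%, 10% or 20% of the 8 × 10 = 80 fecal intervals have no stool, there are 4, 8 or 16 proper zeros that missingness alone does not separate from a loss.

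**Hepatic extraction.** With f the fraction of dose excreted unchanged in urine, E_h_blood = CL(1 − f)/(R_b/p × Q_H). Zeroing a share q of urinary parent lowers CL_R by that share and raises E_h_blood by qf/(1 − f) in relative terms. For q = 0.5, CL_R halves and the rise is 0.51%, 2.63% or 5.56% for f = 1%, 5% or 10%. Protocol 6.2.1 describes the drug as mainly metabolized, which points to the low end.

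**Metabolized fraction.** Fe_met = (total − parent)/total. Assume 90 points total and 10 points parent, so Fe_met = 80/90 = 0.889, and a lost interval of 20 points total with 1 or 5 points parent.
- Only parent missing: 81/90 = 0.900 or 85/90 = 0.944.
- Only total missing: 60/70 = 0.857.
- Both missing: 61/70 = 0.871 or 65/70 = 0.929.

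Fe_met can therefore move in either direction.

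**Do the safeguards mark the total?** The 9.8 flag attaches to the missing concentration, or to a parameter that was not calculated. A zero-filled Ae, Fe or Fe_tot is calculated, so it gets no flag. It is not excluded, so the 7.9.2 footnote does not apply. SAP 7.3 sends other critical missing data to the data review report without requiring a mark on outputs.

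**The case against.** The strongest reply is that much of this is already handled. Zero is only a default, the data review meeting must consider missing PK data case by case, and listings distinguish not done from no sample and also show all eCRF data and deviations. Subjects are resident to 240 h, with toilet access controlled and urine retained. This stands as a reason to expect few losses and some trace of each. It does not supply a criterion for excreta or a mark on the cumulative total.

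On size, the loss rates and dose shares are assumed, and many late intervals may hold little drug. Under the same equal-probability model, 23 intervals share at most 100% of the dose, so a randomly lost one averages at most 100/23 = 4.3 points, or 4.3/8 = 0.54 on the mean. The expected understatement of mean recovery is at most 0.1, 0.5 or 1 point for p = 0.1%, 0.5% or 1%. That is fair: the average effect is small, and the concern is the individual subject and the chart when an early, drug-rich sample has no result.

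On scope, the radioanalysis laboratory calculates total-14C mass balance, and the formulas in 9.4 and 9.5 are worded for parent drug. This limit stands. For labelled parent drug the rule applies directly. SAP section 16 (tables, listings and figures) was not available for this review and may contain a flag.

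A summary with and without affected subjects could seem to conflict with SAP 7.9.1 and Protocol 12.2 on exclusions. It does not, because every subject stays in the main analysis.

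**Conclusion.** The concern holds and should be fixed, with medium confidence. When a voided sample that contained drug has no result, the default understates that subject's cumulative Ae and Fe for the affected matrix and analyte, and Fe_tot, by the interval's full share of dose. The mean of 8 falls by one eighth of that share. A lost urinary parent result also lowers CL_R and slightly raises E_h_blood. Other matrices and analytes are unaffected.

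The conclusion is conditional on such a loss occurring, and the documents do not say how likely that is. Its reach to total-14C recovery assumes that the laboratory follows SAP 9.6. The statement that no flag is required covers SAP sections 1 to 15 only. A void lost from a pooled interval that still has a concentration is a different problem and is not covered here.

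**What to change.** Replace the sentence in SAP 9.6 with these rules:

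1. A result below quantification counts as zero.
2. Interval Ae is zero only when collection records confirm that nothing was voided: fecal void times (Protocol 7.2.1.3), or the urine collection record with volume or weight (Protocol 7.2.1.2, SAP 9.4). The NS code alone is not enough.
3. A voided sample with no concentration is missing, not zero.
4. Flag the affected cumulative Ae and Fe (including Fe_tot), and CL_R, E_h_blood and Fe_met derived from them, as incomplete in listings and tables. Label Ae, Fe and CL_R as lower bounds; for CL_R this fits AUC0-∞ and the SAP 9.4 fallback, which matches the intervals of Ae and AUC. Present summaries for the affected matrix and analyte with and without the affected subjects.
5. State that the same rules bind the radioanalysis laboratory.

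Keep the protocol formula for Fe_met and only flag the result. The affected subject's cumulative sum keeps its value; the change is that it is shown as incomplete. Protocol 12.3.2 leaves missing-data rules to the SAP, so this does not disturb the statement in SAP section 12 that nothing has changed from the protocol.

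The cost is SAP wording, one flag variable and a second summary produced only if a loss occurs. No new data are needed. The drawback is that the second summary may rest on one subject fewer.
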